9.2.2. Adverse Event Summaries

An overall summary of AEs by treatment group will include the following:

- Number (%) of participants reporting any TEAEs
- Number (%) of participants reporting any serious TEAEs
- Number (%) of participants reporting any Grade 3 or higher TEAEs
- Number (%) of participants reporting any treatment-related TEAEs
- Number (%) of participants who temporarily interrupted study drug in part of the treated areas because of TEAEs
- Number (%) of participants who temporarily interrupted study drug in all of the treated areas because of TEAEs
- Number (%) of participants who temporarily interrupted study drug in any of the treated areas because of TEAEs
- Number (%) of participants who permanently discontinued study drug because of TEAEs
- Number (%) of participants who had a fatal TEAE

The following summaries will be produced by MedDRA term (if 2 or fewer participants appear in a table, a listing may be appropriate):

- Summary of TEAEs by SOC and PT
- Summary of TEAEs by PT in decreasing order of frequency
- Summary of Grade 3 or higher TEAEs by SOC and PT
- Summary of Grade 3 or higher TEAEs by PT in decreasing order of frequency
- Summary of serious TEAEs by SOC and PT
- Summary of serious TEAEs by PT in decreasing order of frequency
- Summary of treatment-related TEAEs by SOC and PT
- Summary of treatment-related TEAEs by PT in decreasing order of frequency
- Summary of Grade 3 or higher treatment-related TEAEs by SOC and PT
- Summary of treatment-related serious TEAEs by SOC and PT
- Summary of TEAEs with a fatal outcome by SOC and PT
- Summary of TEAEs leading to dose interruption of study drug in any of the treated areas by SOC and PT
- Summary of TEAEs leading to dose interruption of study drug in part of the treated areas by SOC and PT

- Summary of TEAEs leading to dose interruption of study drug in all of the treated areas by SOC and PT
- Summary of TEAEs leading to discontinuation of study drug by SOC and PT

Subgroup analysis for TEAEs by age categories will also be provided.

Adverse events of interest will be summarized in the following categories:

- Cytopenias
 - Anemia
 - Thrombocytopenia
 - Neutropenia
- Herpes zoster
- Viral skin infections
- Nonmelanoma skin neoplasms
- Liver function test elevations
- Malignancies
- Major Adverse Cardiovascular Events
- Venous and arterial thromboembolic events
- Thrombocytosis and elevated mean platelet volume

9.3. Clinical Laboratory Tests

9.3.1. Laboratory Value Definitions

All laboratory assessments will be performed using a central laboratory except for urine pregnancy tests (as applicable). Laboratory values and change from baseline values will be summarized descriptively by visit and non-numeric test values will be tabulated when necessary.

The baseline value will be determined using the last nonmissing value collected before the first application, prioritizing scheduled assessments for baseline identification over unscheduled visits. The last record before administration in the highest priority will be considered the baseline record. For baseline laboratory candidates with the same date and time in the same priority category, additional rules may be provided after consultation with the medical monitor to delineate which value will be defined as baseline.

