Pregnancy testing	X	X*			X	Section 8.4.4.2; at the indicated visits, only female participants who have reached menarche will undergo a urine pregnancy test. A positive urine test must be confirmed by a serum test. *Day 1 testing will be performed only if the interval between this visit and screening is > 2 weeks.	

Table 3: Schedule of Activities: Vehicle-Controlled Period (Continued)

Visit Day (Range)	Screening	VC Period				Notes and Protocol Section
	Days -28 (+ 7 ^a) to -1	Day 1/ Baseline	Wk 2 (± 3 d)	Wk 4 (± 3 d)	Wk 8 ^b /ET (± 3 d)	

Note: Unscheduled visits may occur at any time at the investigator's discretion, and appropriate clinical and laboratory tests may be performed as clinically indicated.

^a For prior medications that require a 4-week washout period (see Section 5.2, Exclusion Criterion 6b), a 35-day screening period is allowed.

^b Week 8 is the baseline for participants eligible to continue in the LTS period (IGA score = 0-4 and BSA = 0%-20%).

Table 4: Schedule of Activities: Long-Term Safety Period

Visit Day (Range)	LTS Period					Unscheduled Visit	Safety Follow-Up 30 (+ 7) Days After Last Study Cream Application ^a	Notes and Protocol Section
	Wk 12 (± 7 d)	Wk 16, 20, and 24 (± 7 d)	Wk 28, 32, and 36 (± 7 d)	Wk 40, 44, and 48 (± 7 d)	Wk 52/ EOT/ET (± 7 d)			
Administrative procedures								
Contact IRT	X	X	X	X	X	X	X	Section 8.1.3.
Prior/concomitant medications and procedures	X	X	X	X	X	X	X	Section 6.6.
Apply study cream at site	X	X	X	X				Section 6.1; only for participants with active AD lesions at time of visit; apply the first (morning) application under direct site staff supervision.
Weigh and dispense study cream; dispense diary cards	X	X	X	X				Section 6.1 and Section 8.1.4.
Collect and weigh study cream; collect diary cards	X	X	X	X	X			Section 6.1.
Record start and end dates of treatment cycle(s)	X	X	X	X	X			Section 6.1; the start/end date will have been recorded by the participant. The end date should be 3 days after lesions clear; however, if this 3-day window is during a study visit and IGA score = 0, stop treatment and record the date of the study visit as the treatment cycle end date.
Assess compliance	X	X	X	X	X			Section 6.4.
Safety assessments								
AE assessments	X	X	X	X	X	X	X	Section 8.4.1.
Comprehensive physical examination					X			Section 8.4.2.1.

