8.1.2. Screening Procedures

Screening is the interval between signing the ICF/assent and the day the participant is enrolled in the study (Day 1). Informed consent (or assent) must be obtained before performing any study-specific procedures. Screening assessments for determination of eligibility may be performed over a period of up to 28 days, or up to 35 days for participants on prior medications requiring a 4-week washout period as described in Section 5.2 (Exclusion Criterion 6b).

Assessments that are required to demonstrate eligibility may be performed over the course of 1 or more days during the screening process.

Results from the screening visit evaluations will be reviewed to confirm eligibility before enrollment or the administration of study cream. Tests with results that fail eligibility requirements may be repeated once during screening if the investigator believes the results to be in error. For screening assessments that are repeated, the most recent available laboratory results before randomization/treatment assignment will be used to determine eligibility. Additionally, a participant who fails screening may repeat the screening process 1 time if the investigator believes that there has been a change in eligibility status (eg, after recovery from an infection). The participant is not required to sign another ICF if the rescreening occurs within 28 days (or 35 days for participants on prior medications requiring a 4-week washout period) of the previous ICF signature date (screening period).

See Section 5.4 for information regarding screen failures and the rescreening procedure for participants.

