8.4.4. Laboratory Assessments

See [Table 11](#) for the list of clinical laboratory tests to be performed and the SoA (see [Table 3](#) and [Table 4](#)) for the timing and frequency. Day 1 testing will be performed only if the interval between this visit and screening is > 2 weeks. A central laboratory will perform all clinical laboratory assessments for safety (blood chemistries and hematology assessments) [REDACTED]

[REDACTED] Additional testing may be required by the sponsor based on emerging safety data. All Protocol-required laboratory assessments must be conducted in accordance with the Laboratory Manual and the SoA (see [Table 3](#) and [Table 4](#)). Information regarding collection, processing, and shipping of laboratory assessments is provided in the Laboratory Manual.

Clinically significant abnormal laboratory findings are those that are not associated with the underlying disease, unless judged by the investigator to be more severe than expected for the participant's condition. All laboratory tests with values considered clinically significantly abnormal during participation in the study, or within 30 days after the last application of study cream, should be repeated until the values return to normal or baseline or are no longer considered clinically significant by the investigator or medical monitor.

See Section [9.1](#) for information regarding laboratory abnormalities that should be recorded as an AE in the eCRF.

Table 11: Required Laboratory Analytes

Serum Chemistries	Hematology	Serology

• Albumin• Alkaline phosphatase• ALT• AST• Bicarbonate• Blood urea nitrogen or urea• Calcium• Chloride• Creatinine• Glucose• Lactate dehydrogenase• Phosphorus• Potassium• Sodium• Total bilirubin• Direct bilirubin (if total bilirubin is elevated above ULN)	
Complete blood count, including:
 
• Hemoglobin• Hematocrit• Mean corpuscular volume• Platelet count• Mean platelet volume (MPV)• Red blood cell count• Reticulocyte count• White blood cell count 
Differential count, including:
 
• Basophils• Eosinophils• Lymphocytes• Monocytes• Neutrophils	
• HIV antibody 
Pregnancy Testing
 
Female participants who have reached menarche will have a urine test conducted at all required visits. A positive urine test must be confirmed by a serum test.

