4.1.3. Baseline Value

Baseline is the last nonmissing measurement obtained before or on the day of first application of ruxolitinib cream or vehicle cream for the VC period.

For randomized participants not treated with any study drug, baseline is defined as the last nonmissing assessment before or on the day of randomization for all parameters.

For participants who continue in the LTS period, baseline for LTS is defined as follows:

- For efficacy evaluation, baseline is the last nonmissing measurement obtained before or on the day of first application of study treatment in the VC period.
- For safety evaluation, for participants who cross over from vehicle to ruxolitinib cream, baseline is the last nonmissing measurement obtained before or on the day of first application of ruxolitinib cream in the LTS period; for participants on ruxolitinib cream in both periods, baseline is the last nonmissing measurement obtained before or on the day of first application of study treatment in the VC period.

When scheduled assessments and unscheduled assessments occur on the same day and time of the assessment or time of first application is not available, use the following convention to determine baseline:

- If both a scheduled and an unscheduled visit are available on the day of the first application and the time is missing, use the scheduled assessment as baseline.
- If all scheduled assessments are missing on the day of the first application and an unscheduled assessment is available, use the unscheduled assessment as baseline.

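### The SAP's laboratory baseline rule (9.3.1) contradicts its general baseline rule (4.1.3) and can, for a probably small group of children, make a superseded screening result the baseline

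*SAP*

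**What the plan says.** **General rule, SAP 4.1.3.** For the vehicle-controlled period, "Baseline is the last nonmissing measurement obtained before or on the day of first application". Scheduled values are preferred over unscheduled ones under one condition only: "When scheduled assessments and unscheduled assessments occur on the same day and time of the assessment or time of first application is not available". The section also sets a separate safety baseline for the long-term period. Children who cross over from vehicle are re-baselined at their first ruxolitinib application, and children on ruxolitinib throughout keep their original baseline. It makes no exception for laboratory data.

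**Laboratory rule, SAP 9.3.1.** This also begins from the last value before first application, but it selects by "prioritizing scheduled assessments for baseline identification over unscheduled visits" and then adds: "The last record before administration in the highest priority will be considered the baseline record". No same-day limit is given. Consultation with the medical monitor is reserved for records that share date, time and priority class.

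**Protocol 8.1.2.** "Tests with results that fail eligibility requirements may be repeated once during screening if the investigator believes the results to be in error". After a repeat, "the most recent available laboratory results before randomization/treatment assignment will be used to determine eligibility".

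**Protocol 8.4.4.** "Day 1 testing will be performed only if the interval between this visit and screening is > 2 weeks".

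**Protocol Table 3, note.** At unscheduled visits, "appropriate clinical and laboratory tests may be performed as clinically indicated".

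**The concern.** Two sections of one SAP define the same quantity differently, so two programmers working faithfully from it could derive different laboratory baselines for the same child. SAP 11.1 records no change to protocol-defined analyses, and 9.3.1 does not present itself as an exception to 4.1.3.

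The case that matters most is the screening retest. A child who fails a laboratory limit in Exclusion Criterion 3 can be randomized only if the repeat passes, because Protocol Section 5 allows no eligibility waivers. If the repeat is filed as unscheduled and nothing scheduled follows it, 9.3.1 selects the result that the investigator believed to be wrong and that the eligibility decision set aside.

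SAP 9.3.2 builds the CTCAE shift tables from baseline grade to worst later grade, with the baseline category as denominator. A falsely abnormal baseline puts the child in the wrong row and can turn a new abnormality into an apparently old one. Under 4.1.3, a child on ruxolitinib in both periods keeps this baseline in the long-term tables too.

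**Working it through.** The plan gives no figure to reproduce. The check applies both rules, as written, to the same records.

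**Rules**
- 4.1.3: take the latest record up to and including the day of first application. If scheduled and unscheduled records share that day and a time is unavailable, take the scheduled one.
- 9.3.1: if any scheduled record exists, discard the unscheduled ones, then take the latest that remains.

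**Inputs**
- From the documents: the screening limit for absolute neutrophil count (ANC), below which a child is excluded, is 1000/µL (Exclusion Criterion 3c). One repeat is allowed. A Day 1 draw is made only if screening was more than 2 weeks earlier.
- Assumed, for illustration only: all ANC values and draw days. The on-study value is 850/µL throughout.

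**Formula:** change = on-study value − baseline.

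| Case | Pretreatment records (ANC/µL) | Baseline, 4.1.3 | Change | Baseline, 9.3.1 | Change |
|---|---|---|---|---|---|
| A. Retest stored as unscheduled, no Day 1 draw | Day −10 scheduled 900; Day −6 unscheduled 1800 | 1800 | 850 − 1800 = −950 | 900 | 850 − 900 = −50 |
| B. Retest stored as unscheduled, Day 1 draw made | Day −20 scheduled 900; Day −16 unscheduled 1800; Day 1 scheduled 1700 | 1700 | 850 − 1700 = −850 | 1700 | −850 |
| C. Retest stored as a scheduled screening record | Day −10 scheduled 900; Day −6 scheduled 1800 | 1800 | −950 | 1800 | −950 |
| D. Unscheduled draw for another reason, lower than the scheduled one | Day −10 scheduled 1800; Day −6 unscheduled 1100 | 1100 | 850 − 1100 = −250 | 1800 | 850 − 1800 = −950 |

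**Reading the cases**
- In A the change is −950/1800 = −52.8% under 4.1.3 and −50/900 = −5.6% under 9.3.1. The child is newly below 1000/µL under the first rule and already below it under the second.
- In B and C the rules agree.
- In D they disagree in the other direction: 9.3.1 enlarges the fall.

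Case A therefore needs four things together: a failed laboratory limit, a passing repeat, storage of that repeat as unscheduled, and Day 1 no more than 2 weeks after screening. The 1000/µL limit stands in for a grade boundary here, because the documents do not reproduce the CTCAE cut-offs.

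**The case against.** The strongest objection is that the documents do not say how a retest is stored, and that Protocol 8.1.2 leans toward treating it as a screening record. It speaks of repeating screening assessments and lets eligibility assessments spread over several days, and the scheduled screening window in Table 3 runs to Day −1. If retests carry the screening label, case C applies and the two rules agree for retested children. This stands, and it is why the point is conditional. It does not remove the conflict, because Table 3 allows unscheduled laboratory draws and the SAP does not say how they or retests are classified.

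A second objection is that a section on laboratory data may properly set a more specific rule than the general one. It may, but 4.1.3 expressly covers safety evaluation and 9.3.1 does not claim precedence, so the intention is left to guesswork.

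Three stronger readings are tempting and are not supported:
- A reader might infer that baselines are too abnormal in all retested children. Cases B and C show otherwise, and case D shows that unscheduled draws in general can bias either way.
- A reader might infer that cytopenias, listed in SAP 9.2.2 as events of interest, would be hidden. Those tables count reported adverse events and do not use the laboratory baseline. The listings of all and of abnormal laboratory values are also untouched, and the neutrophil interruption thresholds in Protocol Table 9 are absolute counts.
- A reader might infer a bias between arms. The choice of record uses pretreatment data only, so which children are affected should not depend on assignment. Protocol 10.4.3 plans no formal laboratory comparisons between groups.

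**Conclusion.** The contradiction between SAP 4.1.3 and 9.3.1 is plain from the text and should be removed. Its practical effect is small and conditional. Where a retest is stored as unscheduled and no scheduled draw follows, change-from-baseline and CTCAE shift displays can understate worsening for that child. The documents give no count of such children. With several conditions needed at once, the number is probably low. Elsewhere the direction of any error is not fixed. No efficacy analysis is involved. The conclusion rests on reading 9.3.1 literally and, for the retest case, on an assumption about record coding that the documents neither state nor exclude. This is a minor, worthwhile correction.

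**What to change.** Rewrite the baseline paragraph of SAP 9.3.1 so that it:
1. applies the 4.1.3 baseline to laboratory data, that is, the latest available pretreatment value, scheduled or unscheduled;
2. carries over the separate long-term safety baseline for children crossing over from vehicle;
3. keeps the preference for scheduled records only where records fall on the same day and the time is unavailable, as in 4.1.3;
4. states that screening retests are eligible baseline records, however the visit is labeled.

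Point 1 also settles a smaller mismatch: 4.1.3 includes the day of first application, while 9.3.1 says only before it. Protocol Table 3 already requires blood to be drawn before the in-clinic application, so a Day 1 draw taken as planned qualifies under either wording.

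If the sponsor does intend scheduled records to rank first, 4.1.3 should say that 9.3.1 governs laboratory data, the classification of retests should be stated, and a shift table based on the latest pretreatment value should be added.

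The cost is a few sentences in the SAP and the matching change to the laboratory baseline derivation. No new data and no Protocol change are needed. It is best settled before the primary database lock, after which the sponsor is unblinded.

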9.3.2. Laboratory Value Summaries

Clinical laboratory tests, including hematology and serum chemistry, will be performed at the Protocol-specified visits. If specific safety issues arise, additional unscheduled laboratory tests/analyses may be performed at the discretion of the investigator.

All test results and associated normal ranges from central laboratories will be reported in SI units. All tests with numerical values will have a unique unit per test. Any laboratory test results and associated normal ranges from local laboratories will be converted to SI units.

When there are multiple nonmissing laboratory values for a participant's particular test within a visit window, the laboratory value with the smallest laboratory sequence number will be used in by-visit summaries.

Test results will be summarized and listed with available normal ranges, the number and percentage of participants with the laboratory values being low (but never high), normal, high (but never low), and both low and high will be calculated for each test. This shift summary will be produced for each test for the safety population in the VC period, as well as the LTS period for the LTS evaluable population. Shift tables will be presented to show change in CTCAE grade from baseline to worst grade postbaseline as well. The denominator for the percentage calculation will use the number of participants in the baseline category.

Subgroup analysis for laboratory results by age categories will also be provided.

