Targeted physical examination	X	X	X	X		X	X	Section 8.4.2.2; conducted only when indicated by symptoms reported by participant (AEs or other findings); clinically significant abnormalities (in the investigator's judgment) are to be reported as AEs.

Table 4: Schedule of Activities: Long-Term Safety Period (Continued)

Visit Day (Range)	LTS Period					Unscheduled Visit	Safety Follow-Up 30 (+ 7) Days After Last Study Cream Application ^a	Notes and Protocol Section
	Wk 12 (± 7 d)	Wk 16, 20, and 24 (± 7 d)	Wk 28, 32, and 36 (± 7 d)	Wk 40, 44, and 48 (± 7 d)	Wk 52/ EOT/ET (± 7 d)			
Safety assessments (continued)								
Height and weight		X*			X			Section 8.4.3; height should be measured with a stadiometer. *Only at Week 24.
Vital signs	X	X	X	X	X	X	X	Section 8.4.3; vital signs are taken before blood sampling and other procedures.
Disease severity assessments								
Evaluate %BSA affected by active AD lesions	X	X	X	X	X	X	X	Section 8.2.2; evaluate %BSA (excluding the scalp) affected by active AD lesions using the handprint method.
IGA	X	X	X	X	X	X	X	Section 8.2.5.

Table 4: Schedule of Activities: Long-Term Safety Period (Continued)

Visit Day (Range)	LTS Period					Unscheduled Visit	Safety Follow-Up 30 (+ 7) Days After Last Study Cream Application ^a	Notes and Protocol Section
	Wk 12 (± 7 d)	Wk 16, 20, and 24 (± 7 d)	Wk 28, 32, and 36 (± 7 d)	Wk 40, 44, and 48 (± 7 d)	Wk 52/ EOT/ET (± 7 d)			
Laboratory assessments								Blood draws for clinical laboratory tests must be performed before the in-clinic study cream application.
Serum chemistries	X	X*	X*	X*	X	X	X	Section 8.4.4. *Only at Weeks 16, 24, 32, 40, and 48.
Hematology	X	X*	X*	X*	X	X	X	Section 8.4.4. *Only at Weeks 16, 24, 32, 40, and 48.
Pregnancy testing		X*	X*	X*			X	Section 8.4.4.2; at the indicated visits, only female participants who have reached menarche will have urine pregnancy test. A positive urine test must be confirmed by a serum test. *Only at Weeks 16, 24, 32, 40, and 48.

Note: Unscheduled visits may occur at any time at the investigator's discretion, and appropriate clinical and laboratory tests may be performed as clinically indicated.

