ANC < 750/ μ L (without fever); < 1000/ μ L (with fever)	
 Laboratory abnormalities should be confirmed with repeat testing within 48 hours whenever possible and immediate delivery of the laboratory results requested. Study cream applications must be interrupted. At the discretion of the investigator, after consultation with the sponsor, study cream application may be restored once these have resolved.
Any other Grade 3 or higher laboratory abnormality (eg, hemoglobin with the exception of asymptomatic elevations in triglyceride, cholesterol, or amylase)	
 Laboratory abnormalities should be confirmed with repeat testing within 48 hours whenever possible and immediate delivery of the laboratory results requested. Study cream applications must be interrupted. At the discretion of the investigator, after consultation with the sponsor, study cream application may be restored once these have resolved.
Any Grade 4 laboratory abnormality or AST or ALT ($> 20 \times$ ULN)	
 Laboratory abnormalities should be confirmed with repeat testing within 48 hours whenever possible and immediate delivery of the laboratory results requested. Discontinue study cream if laboratory abnormalities are confirmed.

^a In the opinion of the investigator.

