8.7. Unscheduled Visits

Unscheduled study visits may occur at any time medically warranted, including when participants develop new areas of AD. Any assessments performed at those visits should be recorded in the eCRF.

If the participant develops new areas of AD, documentation of the new BSA may occur at an unscheduled visit if appropriate.

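### The by-visit laboratory rule in SAP 9.3.2 selects on an undefined sequence number and gives scheduled draws no priority, so an earlier unscheduled draw in the window can displace the scheduled value

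*SAP*

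**What the plan says.** SAP 9.3.2 sets the rule. Its trigger is "When there are multiple nonmissing laboratory values for a participant's particular test within a visit window", and the instruction is that "the laboratory value with the smallest laboratory sequence number will be used in by-visit summaries". The public text does not say what the sequence number is, whether it follows collection time, or what the laboratory analysis windows are.

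The baseline rule in SAP 9.3.1 differs. It takes the last value before first application, "prioritizing scheduled assessments for baseline identification over unscheduled visits". SAP 4.1.3 likewise prefers the scheduled assessment when both kinds fall on the day of first application and the time is missing. SAP 9.4 and 9.5 summarize weight, height and vital signs by scheduled visit.

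Extra laboratory values are foreseen in several places:

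- Protocol 8.4.4: clinically significant abnormal values "should be repeated until the values return to normal or baseline or are no longer considered clinically significant".
- Protocol 6.5.1, Table 9, for the abnormalities listed there: "Laboratory abnormalities should be confirmed with repeat testing within 48 hours whenever possible".
- Protocol Tables 3 and 4, notes on unscheduled visits: "appropriate clinical and laboratory tests may be performed as clinically indicated".
- Protocol 8.7: "Unscheduled study visits may occur at any time medically warranted, including when participants develop new areas of AD".
- SAP 9.3.2 itself, if safety issues arise: "additional unscheduled laboratory tests/analyses may be performed at the discretion of the investigator".

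**The concern.** A sequence number identifies a record. It does not show whether a value came from the planned draw or how near it lies to the target day. If the number follows collection time, the rule means taking the earliest value in the window, whatever prompted it. If the number follows load order or data source, the rule has no clinical meaning. SAP 9.3.2 provides for local as well as central laboratory results, so a second source is possible.

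At stake is whether the Week 16 column, for example, holds the Week 16 draw for every child who had one. Where it does not, a change from baseline may pair a baseline chosen for being scheduled with a later value that was not. The documents give no reason for treating postbaseline laboratory values differently from baseline values, vital signs and growth.

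**Working it through.** The plan gives no figure to reproduce. The check applies the rule to the protocol's visit calendar.

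**Inputs**

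- Target day. SAP 6.3 puts Week 8 at Day 57, which fits Day = 7w + 1 (7 × 8 + 1 = 57), counted from first application in the vehicle-controlled period.
- Visit windows. ±3 days in the vehicle-controlled period (Protocol Table 3) and ±7 days in the long-term safety period (Protocol Table 4). Using these as analysis windows is an assumption.
- Postbaseline hematology and chemistry draws. Weeks 2 and 8, then Weeks 12, 16, 24, 32, 40, 48 and 52.
- Numbering. Assumed to follow collection time in cases A and B.

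**Case A: retest after the scheduled draw, same window.** Week 12 is Day 7 × 12 + 1 = 85, window 78-92. A confirmatory repeat within 48 hours falls by Day 87. The scheduled value has the smaller number and is kept.

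**Between windows.** Week 16 is Day 7 × 16 + 1 = 113, window 106-120. A repeat on Days 93-105 lies in neither window and enters neither by-visit summary.

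**Case B: unscheduled draw before the scheduled draw, inside its window.** A repeat of the Week 12 test on Days 106-112 comes 106 − 85 = 21 to 112 − 85 = 27 days after an on-target Week 12 draw. It has a smaller number than an on-target Week 16 draw on Day 113 and replaces it. If the Week 16 draw falls on Day s of its window, the exposed days run from 106 to s − 1. That is s − 106 days: none at Day 106, 7 at Day 113 and 14 at Day 120.

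The same arithmetic at other intervals, with on-target draws:

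| Earlier draw | Next draw | Window of next draw | Exposed days | Days after earlier draw |
|---|---|---|---|---|
| Week 2 (Day 15) | Week 8 (Day 57) | 54-60 | 54-56 | 39-41 |
| Week 12 (Day 85) | Week 16 (Day 113) | 106-120 | 106-112 | 21-27 |
| Week 16 (Day 113) | Week 24 (Day 169) | 162-176 | 162-168 | 49-55 |

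**Case C: numbering not chronological.** Either value may be chosen in any window that holds two, including the windows of case A.

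**Dependence on the windows.** If the analysis windows instead met midway between laboratory visits, which the documents do not state, the Week 16 window would open near Day (85 + 113)/2 = 99 and the Week 8 window near Day (15 + 57)/2 = 36. The exposed ranges would be wider. The size of the problem therefore turns on something the public SAP text leaves open.

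**Outputs reached.** The rule governs by-visit summaries: the hematology and chemistry tables in SAP Appendix A (3.3.1.1.1 to 3.3.1.1.3 and 3.3.2.1.1 to 3.3.2.1.3) and, presumably, the by-visit hematology box plots. The box plots listed all cover the vehicle-controlled period, where the table shows three exposed days some six weeks after the Week 2 draw. The exposure is mainly in the long-term safety tables.

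**The case against.** The strongest reply is that the rule is prespecified, ignores the result, and touches nothing that decides a safety conclusion. Protocol 10.4.3 plans no formal laboratory comparisons between groups. CTCAE shifts use the worst postbaseline grade, and the low/high categories classify each participant over all values. Clinically meaningful abnormalities are reported as adverse events, cytopenias and liver test elevations are events of interest, and all values are listed. This stands, and it limits the point to the by-visit displays. It does not justify a selection key that is undefined and inconsistent with the SAP's own baseline convention.

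Three stronger readings are tempting and are not supported.

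- A reader might infer that retests generally replace scheduled values. The one retest that the documents time, confirmation within 48 hours, follows the abnormal sample. Under chronological numbering, the scheduled value survives.
- A reader might infer that the error falls on exactly the children with abnormal results. Repeats are likely to concentrate there, but unscheduled visits also arise for other reasons, such as new areas of dermatitis, and may include laboratory tests. Under Protocol 8.4.4, repeats may also stop once a value is back to baseline or no longer clinically significant, so late repeats need not be common.
- A reader might infer that values taken while cream was interrupted will stand in for on-treatment values. This could happen in a given child, but nothing in the documents shows that it would or how often.

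Nor is SAP 9.3.2 the reverse of the baseline rule: it is silent on scheduled status and does not prefer unscheduled values.

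**Conclusion.** The point holds in limited form. SAP 9.3.2 can select an unscheduled value over the scheduled one for a visit. With chronological numbering and the protocol's visit windows, both assumed, this needs an unscheduled draw inside the window and before the planned draw, such as Days 106-112 ahead of a Day 113 Week 16 draw. Without chronological numbering, the choice is arbitrary wherever a window holds two values.

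The number of participant-visits affected is not in the documents and is probably small. The consequence is some misassigned values in descriptive by-visit tables, mainly in the long-term safety period. Efficacy, type I error, power and the worst-value safety displays are untouched. It is a free improvement and does not threaten a conclusion.

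**What to change.** Replace the sentence in SAP 9.3.2 with a rule of this form: use the scheduled value for that visit; if there is none, use the value closest to the target day; break ties by a stated rule that does not depend on the result. The tie-break needs a deliberate choice, because always taking the later value could favor a recovered retest over the abnormal value before it.

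State the laboratory analysis windows in the same section, since the second step depends on them. Keep unscheduled values in the worst-grade shift tables, the low/high categories and the listings.

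The cost is a short SAP edit and a small programming change. Nothing changes in data collection, sample size or alpha.
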